Free fatty acids (**FFA**) compete with bilirubin for albumin binding sites. There is a long-standing concern that infusion of Intralipid may increase FFA sufficiently to displace bilirubin from albumin and increase serum unbound bilirubin (**UB**) that passes into the brain and causes bilirubin neurotoxicity.³ This concern was heightened by a 2017 report that Intralipid doses of 2-3 g/kg/d were associated with an increase in unbound free fatty acids (**uFFA**) and UB among infants <28 weeks gestation.⁴ Whether these increases resulted in bilirubin neurotoxicity or neurodevelopmental impairment (**NDI**) was not determined. In the commentary⁵ prompted by that report, Amin, Maisels, and Watchko, each a widely respected authority on neonatal hyperbilirubinemia concluded, “The current observations suggest that a more tempered approach to early lipid infusion in neonates ≤28 weeks gestation should be considered, until we have a better understanding of the risks and benefits.”

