2. Any infants with clear evidence of bilirubin neurotoxicity on BAERs and NDI at 22-26 months (including all infants in observational analyses) will have A) moderate to increased mean and peak UB levels in combination with one or more other factors thought increase their susceptibility to bilirubin neurotoxicity; B) a lower peak TSB to UB level (as expected if albumin levels are low or bilirubin is displaced from albumin); C) will have a greater need for mechanical ventilation at 5 days than expected from baseline measures (a potential indicator of bilirubin neurotoxicity at 5 days).

Methods.

Population. Inborn infants <27 weeks' gestation by best obstetric estimate or \leq 750 g birth weight who has no major congenital anomaly or overt nonbacterial infection who has not received Intralipid and whose mother has consented to inclusion of the infant for the NRN Cycled Phototherapy Trial (which warrants higher priority based partly on stipulations in joining the NRN). Mothers of infants <27 weeks gestational age who refuse consent for this randomization control lipid trial may also be approached for consent in the observational arm of this lipid study.

Possibility of inclusion of two other major centers. With the protected time and funding provided by a KL2 award, I hope to add two centers to increase the sample size and generalizability of this pilot study. These centers are 1) the University of Alabama which generally has the largest enrollment in NRN trials and is led by [name] and 2) Stanford where [name] is Visiting Professor and [name], an international leader in studies of bilirubin and PT studies, are based. Both Drs. [name] and [name] have expressed serious interest in joining the pilot.

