Cointerventions. As appropriate for a pragmatic trial, the protein and glucose components of parenteral nutrition (**PN**) will be prescribed by the clinical team following usual care prescribing

guidelines and will likely differ between study groups. The quantities of macronutrients will be recorded during the intervention period (parenteral and enteral, g/kg/day).

Study Assessments. Blood samples for the study will be obtained with blood draws for clinical measurement of TSB levels such that the study will not require additional interventions for blood sampling. The first study blood sample will be obtained on the morning when the newborn is 4 days old (postnatal day 5). Age in days is defined as 0 days old at birth, and 1 day old at midnight on the birthday. Postnatal day 1 is until midnight of the birthday, and postnatal day 2 at midnight on the birthday, etc. Blood samples numbers 2-7 will be obtained on each subsequent morning through postnatal day 14 when a total bilirubin is obtained for clinical purposes as ordered by the clinical team. Bedside nurses collect blood using BD red-top microtainers at the same time that blood is sampled to measure total bilirubin for clinical purposes. A total of up to 6 study blood samples will be obtained within the first 2 weeks from birth, to not exceed total study blood volume of 2mL. (See sample schedule below).

Sample Number	Postnatal Day to Collect	Age (days)	Blood Volume*
*	1 (birthday)	0	0
*	2	1	0
*	3	2	0
1	4	3	0.25mL
2	5	4	0.25mL
3	6	5	0.25mL
4	7	6	0.25mL
5	8	7	0.25mL
6	9	8	0.25mL
Total Blood Vol.			<2 mL

*All samples will be 0.25mL with the exception of the morning after the lipid infusion is advanced to the peak infusion rate (usual group 3 g/kg/day or reduced group 1.5g/kg/day). On this day ONLY, the blood sample volume will be 0.5mL.

Blood Volume and Measurements.

A 0.5 ml will be obtained on the morning after the lipid infusion has been advanced to the peak infusion rate (1.5 or 3.0 g/kg/d).

The priority for measurements for 0.5 ml sample will be:

1. UB [10ul serum] in duplicate [20 ul serum]
2. Albumin [10ul serum] in duplicate [20 ul serum]
3. Unbound FFA complete (60ul serum) in duplicate (120ul serum)

This includes FFA blended estimate

On other days, 0.25 ml blood will be obtained each morning (up to 6 samples).

The priority for measurements for the 0.25 ml samples will be:

1. UB [10ul serum] in duplicate [20 ul serum]
2. Albumin in duplicate [10ul serum] in duplicate [20 ul serum]

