3. Unbound FFA blended estimate [5ul serum] (#1)
4. Unbound FFA complete [60ul serum] (#1)
5. Unbound FFA blended estimate [5ul serum] (#2)
6. Unbound FFA complete [60ul serum] (#2)

The nurse or person obtaining blood for routine TSB levels will collect whole blood at the same time in study-provided red-top microtainer and immediately place the microtainer in a pre-

labeled amber plastic bag provided by the research team. The amber bag containing the sample will be placed in the specified location in the research refrigerator (4 degrees Celcius) as soon as feasible. A member of research team will pick up the specimen within 12 hours, transport the specimen to the UT-Houston McGovern Medical School. In the laboratory space at UT Houston McGovern Medical School, a centrifuge will be used to separate serum which will be labeled and frozen at minus 80 degrees Celsius until samples are shipped in batch to Fluoresprobe Sciences in San Diego, California.

Measurands in each whole blood sample will include concentrations of UB, albumin, total unbound free fatty acids (**uFFA**), and a uFFA profile, which includes concentrations of specific uFFA. These results will not be available with the bedside clinician and will not affect direct patient care. These will be linked with any of the following measurands from the same blood sample measured in the hospital laboratory: TSB, indirect bilirubin, direct bilirubin, albumin, triglyceride, glucose, serum bicarbonate. Additionally, if a blood gas is obtained within 4 hours of this blood draw, the pH from that blood gas will be linked to the sample, providing no intervening ventilator changes were made prior to the blood draw. Other data reflecting general status and severity of illness and/or potentially influencing UB levels will be abstracted from the medical record, including baseline variables such as sex, gestation, anthropometrics, multiple gestation, delivery information, Apgar scores, SNAP-II scores, Z scores at birth, 28 days of life, and 36 weeks postmenstrual age, etc.

Data Management. Data will be entered and stored in a secure UTH REDCap database. Paper logs of data will be secured in a locked cabinet or room.

Outcome Measures. To be compared by treatment group:

Primary outcomes:

- Area under the UB curb with UB concentration >40 nM/L
- BAER wave V latency at 34-36 weeks post menstrual age (or as soon as feasible if the infants if an artifact free BAER cannot be obtained at 34-36 weeks)

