Secondary outcomes:

- Mean UB concentration and proportion of measurements >40 nM/L, peak UB
- Peak UB concentration
- Area under the total unbound FFA (**uFFA**) concentration – time curve; mean FFAu and peak uFFA
- Peak total serum bilirubin (TSB)
- Direct bilirubin > 1.5 mg/dL before discharge
- Macronutrients prescribed (parenteral and enteral protein, fat and carbohydrate, g/kg/day)
- Weight change (g/kg/day) and Z score change from birth through day 28 and at 36 weeks postnatal age
- Relevant data abstracted from the medical record and stored in the existing databases:
 - Serial FiO₂ and ventilator settings (routinely collected generic data)
 - Bronchopulmonary dysplasia (oxygen requirement at 36 weeks PMA)
 - Perinatal and hospital acquired sepsis episodes
 - Other clinical findings potentially related to signs of or susceptibility to bilirubin neurotoxicity
 - Death or NDI as assessed at 24 months PMA
 - Death or hearing loss at 24 months PMA
 - Death or cerebral palsy at 24 months PMA

Cohort analyses (across study groups and any infants in the observational arm) Associations of interest will include:

- UB and death or NDI, unadjusted and adjusted for potential confounders
- UB and wave V latency, unadjusted and adjusted for potential confounders
- Wave V latency and death or NDI, unadjusted and adjusted for potential confounders
- uFFA measured by single probe and total uFFA measured as the sum of individual uFFA
- uFFA and UB
- Total uFFA and individual uFFA(s)

Power and Sample Size. We plan to study sufficient infants at UTH to assess BAERs in 40 infants in each treatment group and have more than 80% power at $P < 0.05$ to identify a difference between groups in wave V latency longer than 0.3 millisecond ($SD = 0.5$ millisecond). This sample size would also afford sufficient power to assess a clinically important difference in UB level.

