Data Analysis. Intention-to-treat analyses will be performed under the supervision of [name]. Generalized linear mixed models will be performed to analyze all outcomes and will include treatment group, PT type (continuous and cycled), as covariates with random effects for study site. Interaction will be assessed for treatment group and PT type. Bayesian analyses will be performed in evaluating differences in treatment effects overall and in different patient subgroups and centers. For the primary outcome and any other continuous outcome, a linear regression model will be used. Binary outcomes will be analyzed with a logistic regression and count data with a Poisson or negative binomial regression model. All priors will be neutral. For binary outcomes, all priors will be centered at RR of 1.0 (indicative of no difference between treatment groups with a 95% prior interval of 0.3-3.0 (in the log RR scale a Normal distribution with mean of 0 and variance of 0.50). A Normal (0,10²) prior will be used for the intercept term and Normal (0,1) for all other variables in the model. For the standard deviation of the center random effect, a half-Normal (0,1) prior will be used. Similar neutral informative priors (based on previous NRN PT trial⁹ where possible) will be used for non-binary outcomes. We will report posterior medians and 95% credible intervals for group differences and relative risks. We will also report posterior probability of benefit/harm for each outcome.

Similar analyses will be conducted for the cohort analyses (including infants in the observational arm).

Data Interpretation. If UB is higher and BAER wave V latency is longer in the UL than the RL group, the findings would likely prompt changes to more conservative use of Intralipid use in the

first 1-2 weeks after birth in extremely preterm infants. If values for UB and BAER wave V latency in the UL group are no higher than the RL group, the findings would support continue use of the UL regimen to provide somewhat greater caloric intake. If UB is higher with no discernible effect on wave V latency, the findings would suggest that the UB level were not high enough to cause bilirubin neurotoxicity with effects lasting to 34-36 weeks. However, findings at 2 years would need to be scrutinized for evidence of adverse neurodevelopmental effects.

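### The exploratory uFFA–UB association has no planned adjustment for albumin, so it cannot separate displacement of bilirubin from low albumin (minor)

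*Combined protocol and SAP*

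**What the plan says.** All references are to the combined protocol and SAP.

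- **Mechanism.** The Rationale states that free fatty acids "compete with bilirubin for albumin binding sites", so that lipid may raise UB.
- **The association.** Outcome Measures, under Cohort analyses, lists six associations of interest. Three carry adjustment wording, for example "UB and wave V latency, unadjusted and adjusted for potential confounders". The item pairing uFFA with UB carries none.
- **The model.** Data Analysis says the outcome models "will include treatment group, PT type (continuous and cycled), as covariates with random effects for study site". It then says: "Similar analyses will be conducted for the cohort analyses (including infants in the observational arm"). No separate covariate list is given for the cohort work, and no model in the document names albumin, TSB or postnatal day.
- **The ambiguity is recognised.** Hypothesis 2B expects a lower ratio of peak TSB to UB in affected infants, "as expected if albumin levels are low or bilirubin is displaced from albumin". Low albumin and displacement are named there as alternative explanations.
- **The data exist.** Study Assessments says: "Measurands in each whole blood sample will include concentrations of UB, albumin, total unbound free fatty acids". Blood Volume and Measurements gives albumin second priority in every sample ("Albumin [10ul serum] in duplicate [20 ul serum"]). Results on the same sample "measured in the hospital laboratory: TSB, indirect bilirubin, direct bilirubin, albumin" are linked to it.

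**The concern.** The randomised comparison can show whether lipid dose changes uFFA and whether it changes UB. It does not relate one to the other. Only the cohort item does, so a reader interested in mechanism will turn to it.

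Followed as written, that item is a regression of UB on uFFA with treatment group, phototherapy type and site. An infant with low albumin has fewer binding sites for both ligands, so both unbound concentrations rise together and the slope is positive even when fatty acids displace no bilirubin. This is bias in the slope; a better standard error does not cure it.

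If the up to six samples per infant are analysed individually, time is a second route. Trends in the same direction inflate the slope, and trends in opposite directions mask it. What is at stake is the meaning of one exploratory result, not the trial's main conclusions.

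**Working it through.** The plan states no figure for this association, so there is none to reproduce. The checks below set the true displacement effect to zero and ask what each model returns. The SDs, mean levels and drifts are assumptions. The sample sizes are from the documents: 80 infants (40 per group with BAERs) and 175 (the extended enrolment). Up to 6 samples per infant are planned.

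**1. Albumin, one value per infant**

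A simple binding model without competition:
- UB ∝ T/(A − T)
- uFFA ∝ F/(4A − F)

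A is albumin, T is TSB and F is total FFA: independent lognormals centred near 380, 90 and 300 µmol/L. Log-SDs are s_A = 0.15, s_T = 0.35 and s_F = 0.3 to 0.5.

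Near the centre, log UB moves with log T and −log A by the same factor, 380/(380 − 90) = 1.31. Log uFFA moves with log F and −log A by 1520/(1520 − 300) = 1.25. The factors cancel in the correlation:

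r ≈ s_A² / √[(s_A² + s_T²)(s_A² + s_F²)]

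- s_F = 0.5: 0.0225 / √(0.145 × 0.2725) = 0.113
- s_F = 0.3: 0.0225 / √(0.145 × 0.1125) = 0.176

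The two-sided 5% rejection rate is about P(Z > 1.96 − atanh(r)·√(n − 3)), plus a negligible other tail.

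| n | s_F | atanh(r)·√(n − 3) | Approximate rate | Simulated, no albumin |
|---|---|---|---|---|
| 80 | 0.5 | 0.1135 × 8.77 = 1.00 | 17% | 16–17% |
| 80 | 0.3 | 0.178 × 8.77 = 1.56 | 35% | 34–35% |
| 175 | 0.5 | 0.1135 × 13.11 = 1.49 | 32% | 29–32% |
| 175 | 0.3 | 0.178 × 13.11 = 2.33 | 65% | 63–64% |

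With albumin and TSB in the model the simulated rate is about 5–7%. In a rerun with albumin alone it was about 5%, so in this set-up TSB adds precision and removes no bias. At s_A = 0.10 the unadjusted rate is 7–21% across the two sample sizes; at 0.20 it is 37–96%.

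**2. Postnatal day, individual samples**

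Assume six daily samples, independent UB and uFFA with within-infant SD 0.7, infant effects removed, and the same drift d (SD per day) in both. Over six days the centred day values have sum of squares 17.5. The within-infant error sum of squares is 5 × 0.49 = 2.45. The spurious within-infant slope is therefore

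17.5d² / (17.5d² + 2.45)

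- d = 0.05: 0.044/2.494 = 0.018. Simulated rate 7% (80 infants) and 9% (175).
- d = 0.1: 0.175/2.625 = 0.067. Rate 27% and 52%.
- d = 0.2: 0.70/3.15 = 0.22. Rate 99% and 100%.

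With day in the model the rate is 4–6%. In a separate simulation on standardised measures, opposite day effects of +0.3 and −0.3 gave a slope of −0.09 when the truth was zero. Combined with albumin effects of 0.4 they cut the spurious slope from +0.16 to about +0.07.

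**3. Postnatal day, infant means**

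If each infant is reduced to a mean over the same days, the drift adds the same constant to every infant and drops out. With drifts of 0.1 and 0.2 the simulated rate was 4.9–5.2%, or 5.2–6.1% when infants contributed 3 to 6 samples at random.

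**4. Does the lipid ramp fall within sampling?**

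In Houston lipid starts the day after the birthday, postnatal day 2, and takes three daily steps, so either regimen's routine maximum is reached on postnatal day 4. The sample table begins on day 4; the Study Assessments text begins on day 5. The scheduled ramp is therefore over at about the time sampling starts. Any day trend must come mainly from the course of bilirubin, from phototherapy, from delayed advances, or from lipid changes allowed from day 8.

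**The case against.** The best case for the plan has five parts.

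- **This is not the trial's displacement test.** A reader might infer that it is, and that a positive result would argue for less lipid. The documents support neither. The lipid effect on uFFA and UB is tested by randomised group under Hypothesis 1, displacement is mentioned in Hypothesis 2B through TSB and UB, and Data Interpretation ties lipid use only to the randomised UB and wave V contrasts. This stands, and it limits the severity.
- **The covariates are unspecified, not excluded.** The model sentence describes the outcome analyses and reaches the cohort only by analogy. It cannot carry over literally, because observational infants have no assigned regimen. This also stands, but an open specification permits the biased model and leaves the choice until after the data are seen.
- **Day bias depends on the unit of analysis.** The listed UB and uFFA measures are mainly per-infant summaries, and on infant means the day problem disappears. This stands, so the day term is needed only for sample-level data.
- **TSB is not shown to confound.** It does so only if it is also related to uFFA. The rule allowing lipid changes from day 8 once phototherapy has been off (TSB below 5 mg/dL) makes some link possible but does not establish one. TSB belongs in the model mainly for precision.
- **The sizes are assumed and modest.** At the central setting r is 0.11–0.18, or 1–3% of variance, and the plan reports posterior medians and credible intervals rather than tests. This is fair: the rejection rates illustrate a shifted estimate and do not forecast a result.

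None of this answers the albumin point.

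**Conclusion.** The gap is real and minor. The only listed analysis relating uFFA to UB directly omits albumin, a shared driver that is measured in the same sample and that the protocol itself names as the alternative to displacement. With no displacement at all, the association would be falsely detected in about 17–35% of studies of 80 infants and 29–64% of studies of 175 if albumin has a log-SD of 0.15. The range is 7–96% for log-SDs of 0.10 to 0.20. These figures rest on an assumed binding model, mean levels and SDs.

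Bias from day trends, of either sign, arises only in a sample-level analysis and depends on assumed drifts. A reader might blame the scheduled lipid advance for such trends, but on the Houston schedule that advance is essentially complete when sampling begins. The randomised UB and wave V comparisons and the stated decision rules do not depend on this association.

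**What to change.** Under Cohort analyses, list the uFFA–UB item as unadjusted and adjusted. In Data Analysis, specify the adjusted model:

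- UB on uFFA, with same-sample albumin, same-sample TSB (mainly for precision), phototherapy type and site.
- If repeated samples are used, add postnatal day and a random intercept for infant. State which unit of analysis is intended.
- Report results with and without the day term. Day can absorb part of a true effect, so neither version should stand alone.
- Report results with and without treatment group. Keeping it removes the randomised part of the variation in uFFA, and observational infants have no assigned group.
- State that the unadjusted association is descriptive and will not be read as evidence of displacement.

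This costs a few sentences and no new data: albumin is already to be measured in each sample, hospital TSB is linked to it, and the sampling day is known. The statistical price is a somewhat wider interval and, in the version with day, possible attenuation of a true effect.

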Enrollment and Randomization. Patients will be approached for informed consent after informed consent has been given or refused for the NRN Cycled PT Trial. Infants for whom informed consent is obtained for this lipid study will be randomized using a variable block size stratified by study site and phototherapy use (continuous or cycled which may affect UB level) to either UL or RL using a web-based computerized program (REDCap). Lipid and phototherapy use are concurrent. Mothers who refuse consent infants for this lipid trial will be asked if they would consent for their infant to be included in the observational component of this study so that UB levels can be related to BAERs and 2-year outcomes. In the observational component Intralipid infusions will be at the attending physician's discretion and care would be altered only by collection of the small amount of blood (\leq 2 mL total) as for participants randomized to UL or RL.

Treatment Regimen.

UL regimen: Intralipid will be started at 1 g/kg/day and routinely advanced by 1 g/kg/day each day to a max of 3 g/kg/day as per usual clinical practice.

RL regimen: Intralipid will be started at 0.5 g/kg/day and routinely advanced by 0.5 g/kg/day each day to a max of 1.5 g/kg/day (half rate of usual clinical practice).

The assigned treatment regimen (UL or RL) will remain in effect for a minimum of 7 days and a maximum of 14. On postnatal day 8-14, the Intralipid preparation and dosage maybe changed at the discretion of the clinical team if phototherapy has been off for \geq 48 hours (TSB <5 mg/dL). (After that point, the Intralipid preparation and dosage maybe changed at the discretion of the clinical team). Throughout the study period, the infusion rates for both regimens may be decreased, and advances may be delayed for reason of lipid intolerance providing the justification is documented in the daily progress note. (Each study site should strive to standardize criteria for lipid intolerance so as to minimize the likelihood of using different criteria for the treatment groups). Intralipid infusions will be routinely initiated on specified day after the birthday as per the routine in the study site; this will be the first day after the birthday in Houston. The dates and times of start, stop, and changes in infusion rates will be recorded.

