Data Safety and Monitoring. [name], the study statistician, will conduct an interim analysis of mortality when half the planned sample size has been discharged from the neonatal ICU. If there is a Bayesian posterior probability >99% (assuming a neutral prior probability), the study statistician ([name]), will notify the [name], Medical Director of the CMHH Neonatal ICU and the Director of the Neonatology Division. Unless there are important chance differences between treatment groups in baseline risk factors that are known to influence outcomes of extremely premature infants (birth weight, gestational age, sex, multiple births (twins, triplets), antenatal steroids, high ventilator settings) and that could account for differences in outcome, she would contact [name]. They would decide whether to halt enrollment in the study.

Predischarge outcome date will of course be entered into the study database for each infant once he/she is discharged from the NICU. The rationale for the stopping guideline is that impairment is likely to be a persisting problem and that other neonatal outcomes short of death (IVH, NEC, BPD) are short term outcomes less important than impairment or death. Were we performing frequentist analysis, the stopping guideline would be based on a $p < 0.01$ (two-tailed).

References

¹ Hay WW. Aggressive nutrition of the preterm infant. *Curr Pediatr Rep* 2013;1:doi:10.1007/s40124-013-0026-4.

² Simmer K, Rao SC. Early introduction of lipids to parenterally-fed preterm infants. *Cochrane Database Syst Rev*. 2005 Apr 18;(2):CD005256.

³ Effect of free fatty acids on bilirubin-albumin binding affinity and unbound bilirubin in premature infants. Amin SB. *JPEN J Parenter Enteral Nutr*. 2010 Jul-Aug;34(4):414-20

⁴ Hegyi T, Kleinfeld A, Huber A, Weinberger B, Memon N, Shih WJ, Carayannopoulos M, Oh W. Effects of Soybean Lipid Infusion on Unbound Free Fatty Acids and Unbound Bilirubin in Preterm Infants. *J Pediatr*. 2017 May;184:45-50

⁵ Amin SB, Maisels MJ, Watchko JF. Early Lipid Infusions and Unbound Bilirubin in Preterm Neonates: A Cause for Concern?. *J Pediatr*. 2017 May;184:6-7

⁶ Shapiro SM, Popelka GR. Auditory impairment in infants at risk for bilirubin-induced neurologic dysfunction. *Semin Perinatol*. 2011;35(3):162-170.

⁷ Wennberg RP, Ahlfors CE, Bickers R, McMurry CA, Shetter JL. Abnormal auditory brainstem response in a newborn infant with hyperbilirubinemia: improvement with exchange transfusion. *J Pediatr*. 1982;100(4):624-626.

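### No model accounts for sibling correlation and no sibling allocation rule is given: treatment intervals lose a little precision or depend on that rule, and cohort intervals are probably slightly too narrow

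*Combined protocol and SAP*

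**What the plan says.** The Data Analysis section sets one framework: "Generalized linear mixed models will be performed to analyze all outcomes". Treatment group and phototherapy type enter as covariates, "with random effects for study site". The only variance-component prior matches that structure: "For the standard deviation of the center random effect, a half-Normal (0,1) prior will be used". The section then extends the approach: "Similar analyses will be conducted for the cohort analyses (including infants in the observational arm").

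Several passages show that siblings can be in the data:

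- The Population section does not exclude multiples.
- The baseline variables listed under Blood Volume and Measurements include "multiple gestation, delivery information".
- Data Safety and Monitoring names "multiple births (twins, triplets") among the baseline factors that influence outcome.

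On allocation, Enrollment and Randomization says that consented infants "will be randomized using a variable block size stratified by study site and phototherapy use". The unit named is the infant. Nothing says whether siblings are allocated separately, together or to opposite arms. No family term, estimating-equation approach or cluster-robust variance appears anywhere.

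**The concern.** Siblings share gestational age, antenatal exposures, much of their genetic make-up and often their early care. Their unbound bilirubin (UB), wave V latency and two-year outcomes are therefore likely to be correlated. A site effect does not absorb this, because it gives all infants at a centre the same shift. Given site and covariates, the stated model treats co-twins as independent.

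At stake are the width of the credible intervals and the posterior probabilities of benefit or harm, including those for both primary outcomes, and the precision of the cohort associations between UB, wave V latency and death or neurodevelopmental impairment (NDI). Precision matters to this sponsor: the text after Power and Sample Size justifies enlarging enrolment to 175 partly by a tighter interval. If the handling of siblings is not fixed in advance, it can also be chosen after results are seen.

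**Working it through.** **Inputs from the plan.** 40 infants per group, a difference of 0.3 ms and SD 0.5 ms (Power and Sample Size); enlarged enrolment of 175.

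**Assumptions, not in the plan.** Share *w* of infants with an enrolled co-twin, 20-30%; within-pair correlation (ICC) *ρ*, 0.3-0.7; pairs only, no triplets. The plan is Bayesian and sets no 5% decision rule for outcomes, so error rates and coverage serve only as a yardstick for interval width.

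**1. The plan's own figure, infants independent.** SE = 0.5 × √(2/40) = 0.1118 ms, and 0.3/0.1118 = 2.683. Two-sided power is Φ(2.683 − 1.960) = 76.5%; one-sided it is Φ(2.683 − 1.645) = 85.0%. The stated power above 80% is met only one-sided, and the plan does not state the sidedness. That is a separate matter; the figure is used here as the no-clustering baseline.

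**2. Siblings share an arm.** Variance ratio = 1 + *wρ*; actual error = 2[1 − Φ(1.96/√ratio)].

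- Low end: 1 + 0.2 × 0.3 = 1.06; SE ratio 1.03; error 5.7%.
- High end: 1 + 0.3 × 0.7 = 1.21; SE ratio 1.10; error 7.5%.
- Two-sided power at 40 per group falls from 76.5% to between 74.1% and 68.4%.

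**3. Siblings split between arms.** Variance ratio = 1 − *wρ*, from 0.94 to 0.79. The same error formula gives 4.3% down to 2.7%, so intervals are too wide.

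**4. Infants randomised individually.** Concordant and discordant pairs roughly cancel, so the variance ratio is about 1. What is lost is efficiency. Relative to a singleton, each infant carries information 1/(1 + *ρ*) in a same-arm pair and 1/(1 − *ρ*) in an opposite-arm pair. With equal chances the average is 1/(1 − *ρ*²). The SE with a family effect, divided by the SE without, is therefore 1/√(1 − *w* + *w*/(1 − *ρ*²)).

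- *w* = 0.25, *ρ* = 0.5: 1/√1.083 = 0.961, a 3.9% smaller SE.
- *w* = 0.30, *ρ* = 0.5: 1/√1.100 = 0.953, a 4.7% smaller SE.
- At 40 per group, 0.112 ms becomes about 0.107 ms.
- The gain is sensitive to *ρ*: 1/√1.020 gives 1% at *w* = 0.2, *ρ* = 0.3, and 1/√1.288 gives 12% at *w* = 0.3, *ρ* = 0.7.

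The formula takes the family variance as known, so the realised gain will be slightly smaller; 3-5% is a fair summary at an ICC of 0.5.

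**5. Simulation check.** Coverage of an ordinary 95% interval that ignores family, 20,000 runs per setting:

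| N | *w* | *ρ* | Individual | Same arm | Opposite arms |
|---|---|---|---|---|---|
| 80 | 0.3 | 0.5 | 94.8% | 93.2% | 96.7% |
| 80 | 0.3 | 0.7 | 95.0% | 92.5% | 97.2% |
| 175 | 0.3 | 0.5 | 94.9% | 93.2% | 96.6% |
| 175 | 0.3 | 0.7 | 95.1% | 92.5% | 97.0% |

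**6. Cohort associations.** Here siblings can be alike in exposure (correlation *ρx*) and in outcome (*ρy*). Variance ratio ≈ 1 + *w ρx ρy*. With *w* = 0.3:

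- both correlations 0.5: 1 + 0.3 × 0.25 = 1.075; simulated coverage at N = 175 is 94.4%;
- both correlations 0.7: 1 + 0.3 × 0.49 = 1.147; simulated coverage is 93.2%.

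The cohort size of 175 is itself an assumption, since observational infants could change it.

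**The case against.** The strongest reply is that the plan names the infant as the unit of randomisation. On that reading coverage of the treatment effect is near nominal, and a family term is a refinement rather than a correction. This stands. A reader might infer from the missing term that the treatment-effect intervals are wrong whenever siblings are enrolled. The documents do not support that. Inflated error requires siblings to be placed in the same arm, and nothing in the plan says they are.

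The inputs are also assumed. Recorded multiple gestation does not mean that both siblings contribute: each must be eligible, consented and, for latency, alive to be tested. This stands too, and is why only ranges are given.

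Objections to the remedy narrow it without defeating it:

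- Mother-clustered standard errors do not produce the credible intervals and posterior probabilities that the plan promises, so they are not the best choice here.
- In a logistic model a family intercept changes the estimand to a family-conditional odds ratio, whereas the plan reports relative risks. With most families contributing one infant, the family SD would be largely prior-driven. At an SD of 0.8, the mean of a half-Normal(0,1), the usual approximation makes the conditional log odds ratio √(1 + 0.346 × 0.64) = 1.105 times the marginal one, about 10% larger.

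Neither difficulty of estimand applies to the linear models for the two continuous primary outcomes. Nor does individual randomisation of lipid dose protect the cohort analyses, where the exposure of interest is a measured value that siblings can share.

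**Conclusion.** The point holds as a cheap improvement. Site is the only random effect, multiples can be enrolled, and sibling correlation is therefore ignored.

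- **Treatment comparison.** Under individual randomisation validity is essentially intact, and about 3-5% of the SE is lost (25-30% of infants in enrolled pairs, ICC 0.5). Shared allocation would give error of about 5.7-7.5% (20-30% share, ICC 0.3-0.7). Split allocation would make intervals conservative. The plan does not settle which applies.
- **Cohort analyses.** Intervals are likely modestly too narrow whatever the rule: coverage is about 93-94% under the assumed inputs.

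The plan gives neither the sibling share nor the within-family correlation, so all sizes are conditional, and under these ranges they are modest. It would go too far to call the primary results invalid. What is established is that a better-fitting model is readily available and the allocation rule is missing.

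**What to change.** - State in Enrollment and Randomization whether siblings are randomised individually or together, as was actually done.
- Add a random intercept for family (mother) to the linear models for the continuous outcomes, including both primary outcomes, and to the cohort models. Give its SD a stated weakly informative prior on the scale of the outcome. The half-Normal(0,1) used for centre should not be carried over unchanged, since latency (SD 0.5 ms) and a UB area are on different scales.
- For binary outcomes, either include the family effect and report relative risks averaged over it, or make it a prespecified sensitivity analysis.
- Report how many families contribute more than one infant.

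The cost is a few sentences and a variable linking siblings. The plan lists multiple gestation but no family identifier; since mothers give consent, the link should be recoverable, though that is an inference. Fitting will be slower, and the family variance will be weakly estimated because most families contribute one infant, so a check of sensitivity to its prior is sensible.
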